### 9.2. Adverse Events

Investigators are responsible for monitoring the safety of subjects who have entered this study and for alerting Lilly or its designee to any event that seems unusual, even if this event may be considered an unanticipated benefit to the subject.

The investigator is responsible for the appropriate medical care of subjects during the study.

Investigators must document their review of each laboratory safety report.

The investigator remains responsible for following, through an appropriate health care option, AEs that are serious or otherwise medically important, considered related to the IP or the study, or that caused the subject to discontinue the IP before completing the study. The subject should be followed until the event resolves, stabilizes with appropriate diagnostic evaluation, or is reasonably explained. The frequency of follow-up evaluations of the AE is left to the discretion of the investigator.

After the informed consent form is signed, study site personnel will record, via eCRF, the occurrence and nature of each subject's preexisting conditions. Additionally, site personnel will record any change in the condition(s) and the occurrence and nature of any AEs.

The investigator will interpret and document whether or not an AE has a reasonable possibility of being related to study treatment, study device, or a study procedure, taking into account concomitant treatment or pathologies.

A "reasonable possibility" means that there is a cause and effect relationship between the IP, study device, and/or study procedure and the AE.

Planned surgeries should not be reported as AEs unless the underlying medical condition has worsened during the course of the study.

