#### **9.2.1.1. Adverse Device Effects**

Any AE believed to be related to an issue with the investigational device (AI) or to the use of the study device (PFS) is considered an adverse device event. These events must be clearly indicated as such in the eCRF, and reported to the sponsor. A PC should also be reported.

For the purpose of this protocol, “unanticipated” adverse device effect means any serious adverse event alleged to be associated or related to the device, and which has been confirmed as such by the sponsor. The SAE relatedness must be clearly indicated as such in the eCRF, and reported to the sponsor within 24 hours of site knowledge of the event. A PC should also be reported.

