### **10.3.1. Safety Analyses**

#### **10.3.1.1. Clinical Evaluation of Safety**

All IP and protocol procedure AEs and PCs will be listed, and if the frequency of events allows, safety data will be summarized using descriptive methodology.

The incidence of symptoms for each treatment will be presented by severity and by association with IP as perceived by the investigator. Symptoms reported to occur prior to study entry will be distinguished from those reported as new or increased in severity during the study. Each symptom will be classified by the most suitable term from the medical regulatory dictionary.

The number of IP- and device-related SAEs and any related PCs will be reported.

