## **9. STATISTICAL METHODOLOGY**

### **9.1 General**

Data listings will be provided for all data that is databased. Summary statistics and statistical analysis will only be presented for data where detailed in this SAP. For continuous data, summary statistics will include the arithmetic mean, arithmetic standard deviation (SD), median, minimum, maximum, and N. For log-normal data (e.g. the PK parameters: AUCs and  $C_{max}$ ) the geometric mean and geometric coefficient of variation (CV%) will also be presented. For categorical data, frequency count and percentages will be presented. Data listings will be provided for all subjects up to the point of withdrawal, with any subjects excluded from the relevant population highlighted. Summary statistics and statistical analyses will generally only be performed for subjects included in the relevant analysis population. For the calculation of summary statistics and statistical analysis, unrounded data will be used.

Mean change from baseline is the mean of all individual subjects’ change from baseline values. Each individual change from baseline will be calculated by subtracting the individual subject’s baseline value from the value at the timepoint. The individual subject’s change from baseline values will be used to calculate the mean change from baseline using a SAS procedure such as Proc Univariate.

Data analysis will be performed using SAS® Version 9.4 or greater.

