## **9.4 Safety and Tolerability Assessments**

### **9.4.1 Adverse events**

Where changes in severity are recorded in the Case Report Form (CRF), each separate severity of the AE will be reported in the listings, only the most severe will be used in the summary tables. A pre-existing condition is defined as an AE that starts before the subject has provided written informed consent and is ongoing at consent. A non-treatment emergent AE is defined as an AE which starts after informed consent but prior to dosing. A treatment-emergent AE is defined as an AE which occurs postdose or which is present prior to dosing and becomes more severe postdose.

All AEs will be listed. Treatment-emergent AEs will be summarized by treatment, severity and relationship to the study drug. The frequency (the number of AEs, the number of subjects experiencing an AE and the percentage of subjects experiencing an AE) of treatment-emergent AEs will be summarized by treatment, Medical Dictionary for Regulatory Activities (MedDRA) version 20.1 system organ class and preferred term. The summary and frequency AE tables will be presented for all causalities and those considered related to the study drug. Any serious AEs will be tabulated.

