#### **9.4.12 Other assessments**

All other safety assessments not detailed in this section will be listed but not summarized or statistically analyzed.

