### **11. CHANGES FROM THE PROTOCOL SPECIFIED STATISTICAL ANALYSES**

There were no changes from the protocol specified statistical analyses.

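### SAP 9.4.1 splits adverse events by relationship to the drug only and omits the device-related SAE and product-complaint outputs that protocol 10.3.1.1 commits to

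*SAP*

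**What the plan says.** Protocol 9.2 asks the investigator to document whether each AE has a "reasonable possibility of being related to study treatment, study device, or a study procedure". Of adverse device events, protocol 9.2.1.1 says "These events must be clearly indicated as such in the eCRF, and reported to the sponsor", and it asks for a product complaint (PC) as well. The Schedule of Activities has device-related AEs and PCs collected in both parts.

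Protocol 10.3.1.1 plans listings of AEs and PCs, with descriptive summaries where event numbers permit. It splits symptom incidence by severity and by association with the investigational product. It then adds, without condition: "The number of IP- and device-related SAEs and any related PCs will be reported".

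SAP 9.4.1 says "Treatment-emergent AEs will be summarized by treatment, severity and relationship to the study drug". It adds frequency tables by system organ class and preferred term, and a table of serious AEs. On causality: "The summary and frequency AE tables will be presented for all causalities and those considered related to the study drug". Device relationship is not mentioned in the SAP. PCs appear once, in the design description (SAP section 5), with no analysis attached.

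Three other SAP statements decide what follows from that silence:
- SAP 9.1: "Summary statistics and statistical analysis will only be presented for data where detailed in this SAP".
- SAP 9.4.12: "All other safety assessments not detailed in this section will be listed but not summarized or statistically analyzed".
- SAP 11: "There were no changes from the protocol specified statistical analyses".

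**The concern.** This is a study of delivery presentations. Part A bridges two pre-filled syringe presentations, and Part B compares slow and fast autoinjector delivery. TEAE incidence is a primary endpoint in both parts. Protocol 3.3 itself names local device-based risks, such as bleeding and bruising.

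An event that the investigator attributes to the device but not to the antibody is absent from the only table restricted to related events. A reader of the report who wants to know how often each presentation caused device-related events or complaints would have to work it out from listings. The protocol told that reader to expect at least part of the answer as a reported number.

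**Working it through.** No alpha, power or variance enters this point, so the check compares what is collected, what is promised and what is planned.

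1. **Collected.** Relationship to treatment, device and procedure is documented for each AE (protocol 9.2). Adverse device events are marked in the eCRF (protocol 9.2.1.1). PCs go on study-specific complaint forms sent to the sponsor (protocol 9.2.2).

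2. **Promised in protocol 10.3.1.1.** (a) The number of product-related and device-related SAEs, with related PCs: unconditional. (b) A descriptive summary of AEs and PCs: conditional on frequency. (c) Symptom incidence by association with the investigational product: no device split is promised here.

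3. **Planned in SAP 9.4.1.** Item (c) is met. For (a), serious AEs are tabulated, but no device attribution or PC count is named. For (b), AEs are summarized and PCs are not.

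4. **Can a default fill the gap?** No. SAP 9.1 ties summaries to what the SAP details, and SAP 9.4.12 makes other safety assessments listing-only. SAP section 3 says the SAP replaces the protocol's statistical considerations and will identify substantial differences. SAP 11 identifies none.

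5. **Is it a version effect?** The SAP was written against protocol amendment (a). The summary for amendment (b) lists a change to section 10.3.7 only, so a later edit to 10.3.1.1 does not explain the mismatch.

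6. **What differs within each planned contrast?** Every regimen uses 125 mg/mL (protocol Tables AMAQ.2 and AMAQ.3).
 - Test 1 vs Reference: 1 × 2 mL × 125 = 250 mg vs 2 × 1 mL × 125 = 250 mg.
 - Test 2 vs Test 3: 250 mg vs 250 mg.
 - Test 4 vs Test 5: 1 × 1 mL × 125 = 125 mg vs 125 mg.

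 Dose per administration and concentration are fixed within each contrast; presentation or speed varies. Dose does differ between the two Part B arms (125 vs 250 mg), but no pairwise comparison of those arms is among those listed.

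7. **What each table would show: illustration only, with assumed counts.** Suppose 3 of 18 subjects on one regimen and 0 of 18 on the other have an event judged device-related but not drug-related.
 - Drug-related table: 0/18 vs 0/18, that is 0% vs 0% from these events.
 - All-causality table: the 3 subjects are counted under that regimen and the relevant preferred terms, mixed with events of every other cause.
 - A device-related column: 3/18 = 17% vs 0/18 = 0%.

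The events are not lost from the tables. What is lost is the ability to pick them out.

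**The case against.** The strongest reply is that randomization already does the work. Dose and product are equal within each contrast, so the all-causality comparison by treatment targets the presentation or speed effect without anyone's attribution. Device attribution is an investigator's judgement in an open-label trial; in Part B only the subjects are kept unaware of speed (protocol 7.3). This stands. It is why the device-related column is useful description and not essential to the comparison.

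A reader might infer that the SAP dropped a promised device-related TEAE table. The documents do not support that: the protocol's own split of symptom incidence is by association with the investigational product.

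A reader might also infer that nothing device-relevant is summarized. That is not so either. Injection-site findings (SAP 9.4.7), pain (9.4.8), injection duration (9.4.9) and the autoinjector use questionnaire (9.4.10) all have summaries. None is a table of device-attributed events or complaints, however, and bleeding is only listed.

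It can also be said that a device-related SAE count could be read from the serious AE table and the listings. Serious events are likely to be rare, since protocol 3.2 reports none in the two earlier studies, and protocol 10.3.1.1 does not ask for the count by treatment. That reduces the practical loss. It does not turn an unplanned count into a planned one, and it does nothing for a PC summary. The table shells were not available to check, but SAP 9.1 limits what they could add.

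**Conclusion.** The point holds as a gap between SAP and protocol. The count of device-related SAEs with related PCs, and the conditional PC summary, have no planned output for any of the 6 regimens, and SAP 11 says nothing changed. The size is modest: events are still collected, still listed where databased, and TEAEs are still counted in the all-causality tables. No numerical bias in any planned estimate is claimed.

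The conclusion rests on two readings: that the protocol's conditional safety summary includes PCs, which the same sentence names, and that SAP 9.1 governs the table shells.

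It would go too far to say that the trial can already attribute every event and complaint to a single injection. Part B involves about 36 × 2 = 72 injections, but no section describes an eCRF field linking an AE to the Day 1 or Day 2 injection, or says that complaint forms are databased per injection. The number of local findings that would reach a device-related column is also uncertain. Protocol 9.2.1.4 says scheduled injection-site assessments are not repeated on the AE form, while 9.4.4.4 says injection-site reactions are captured as AEs.

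**What to change.** In SAP 9.4.1:
- add counts, by treatment, of device-related SAEs and of product complaints, identifying the complaints related to those SAEs;
- add a device-related column beside the drug-related one in the TEAE summary and frequency tables, using the attribution already recorded in the eCRF and the same assignment of events to treatment as the existing tables.

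Correct SAP 11 to match. If the sponsor prefers not to produce the counts, SAP 11 should at least declare the omission and give the reason.

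Procedure-related columns are optional. Per-injection attribution in Part B should be specified only if the sponsor confirms that the eCRF links events and complaints to an injection. The sponsor should also confirm that complaint data will be in the analysis database.

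The cost is SAP wording and a few descriptive tables, with no new AE attribution to collect. The downside is that the tables rest on open-label investigator attribution and will probably hold low counts, so they should be read as description. The listing-only treatment of bleeding in SAP 9.4.7 is a separate matter that this change does not resolve.

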### **9.4.2 Concomitant medication**

Concomitant medication will be coded using the WHO drug dictionary (Version September 2017). Concomitant medication will be listed.

### **9.4.3 Clinical laboratory parameters**

All clinical chemistry and hematology data will be summarized by parameter and treatment, and listed. Urinalysis data will be listed. Additionally clinical chemistry, hematology and urinalysis data outside the reference ranges will be listed.

Values for any clinical chemistry, hematology and urinalysis values outside the reference ranges will be flagged on the individual subject data listings.

### **9.4.4 Vital signs**

Vital signs data will be summarized by treatment together with changes from baseline, where baseline is defined as Day 1 predose.

Furthermore, values for individual subjects will be listed.

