## Study Schedule Protocol I6T-MC-AMAQ – Part B

Procedure	Screening	Days							Comments
		-28 days	-1	1	2	3	15 ±2d	43 ±2d	
Informed consent	X								
Review / confirm inclusion/exclusion criteria	X	X							Any time prior to dosing.
Subject admission to CRU		X							
Subject discharge from CRU					X				
Outpatient visit	X					X	X	X	
Randomization			X						Subjects randomized to 1-mL or 2-mL AI arm, and then further randomized within the arm in respect to sequence of injection speed on Days 1 and 2 (slow/fast or fast/slow).
Injection training		X							
LY3074828 injection			X	X					Doses self-administered.
Stopwatch and video recording			X	X					Stopwatch is the source for injection duration capture. Video recording for device functionality.
AI Use Assessment Questionnaire			X	X					Clinical staff who observe the subject's self-injection with the AI will fill out the AI Use Assessment Questionnaire
Medical history	X								
Weight, height, and BMI	X								
Vital signs: blood pressure, pulse rate, temperature (hour)	X	X	0, 6	0, 6	24	X	X	X	Times with respect to start of dosing. Single ECGs to be collected. Zero-hour collection within 30 minutes before dosing. Time allowance for 6- and 24-hour time points: ±30 and ±90 minutes, respectively. For vital sign assessments, temperature need only be included at predose and when clinically indicated.
12-lead ECG (hour)	X		0	0	24			X	
Physical examination / medical assessment	X	X			X			X	Full physical examination/medical assessment at screening. Symptom-directed physical examination/medical assessment at all other time points, and as deemed necessary by the investigator.

Procedure	Screening ≤28 days	Days							Comments
		-1	1	2	3	15 ±2d	43 ±2d	86/ED ±3d	
AE review	X	X	X	X	X	X	X	X	AE only after signing ICF. Product complaints and device-related AEs collected as appropriate.
QuantiFERON®-TB Gold test	X								
Serology	X								See Appendix 2 for test details.
Ethanol test and urine drug screen	X	X							May be repeated at the discretion of the investigator. Ethanol test may be either breath or urine testing. See Appendix 2 for test details.

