## 5.4. Scientific Rationale for Study Design

Conducting the study in healthy subjects mitigates the potential confounding effects of the disease state and concomitant medications in patients. Healthy subjects are frequently used in the assessment of bioavailability of both small and large molecules.

For Part A, single doses of LY3074828 and the PK sampling time points have been selected to generate PK profiles sufficient to fulfill the study objectives. As the primary endpoints for Part A of this study are PK-related and are not subject to bias, it is not considered necessary for this study to be blinded. Subjects and site staff will be aware of the administration route and treatment.

For Part B, only an evaluation of safety and tolerability of, and pain associated with, the investigational AI administrations is intended. Pharmacokinetic samples are collected only in conjunction with immunogenicity samples to provide concentrations of LY3074828 to aid in the interpretation of ADA data if needed.

For Part A, a parallel-group design was chosen because a crossover design is impractical for compounds that have long half-lives, such as monoclonal antibodies. Additionally, a crossover study design could confound PK data if subjects develop neutralizing ADAs.

For Part B, a crossover design was chosen as PK analysis is not an endpoint and a relatively short time between injections will allow a more accurate comparison of injection-site pain by subjects

Monoclonal antibody therapy has been associated with hypersensitivity reactions, including injection-site reactions. Follow-up details on injection-site reactions will be collected by the investigative site regarding the severity, duration, type, and timing of the start of the event in relation to the start of study drug administration in order to further characterize these events.

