#### **10.3.1.2.4. *Statistical Evaluation of Other Safety Parameters***

Other safety parameters that will be assessed include clinical laboratory parameters, vital signs, and ECG parameters. The parameters, and changes from baseline (predose) where appropriate, will be listed and summarized using standard descriptive statistics. Additional analyses will be performed if warranted upon review of the data.

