### Part B

- Tests 2 and 3: 250 mg LY3074828 solution formulation, 1 x 2-mL 125-mg/mL AI slow injection (Test 2; targeting approximately 13-second injection time) and fast injection (Test 3; targeting approximately 5-second injection time) using an investigational 2-mL AI
- Tests 4 and 5: 125 mg LY3074828 solution formulation, 1 x 1-mL 125 mg/mL AI slow injection (Test 4; targeting approximately 7-second injection time) and fast injection (Test 5; targeting approximately 4.5-second injection time) using an investigational 1-mL AI

For Part A, subjects will report to the clinical research unit (CRU) on Day -1 and will remain at the CRU until the scheduled procedures have been completed on Day 2. After randomization to either a 2 x 1-mL or a 1 x 2-mL 125-mg/mL PFS dose regimen, study drug will be administered by investigative site staff by SC injection in the abdomen in the morning of Day 1 after an overnight fast.

For Part B, subjects will report to the CRU on Day -1 and will remain at the CRU until the scheduled procedures have been completed on Day 3. Subjects will be randomized to receive, on Days 1 and 2, either a 1 x 1-mL or a 1 x 2-mL 125-mg/mL AI dose regimen. The allocated AI dose regimen will be self-administered by slow and fast SC injection(s) on consecutive days (sequence randomized) in the abdomen after an overnight fast.

Safety and tolerability will be explored by clinical laboratory tests, vital sign measurements, 12-lead electrocardiograms (ECGs), recording of adverse events (AEs) and product complaints, physical examinations/medical assessments, immunogenicity, and injection-site assessments. Pain assessments will be made using the Short Form McGill Pain Questionnaire (SF-MPQ), which includes a subject-assessed injection-site pain visual analog scale (VAS).

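### In Part B, SAP 9.4.4 measures vital-sign change after the Day 2 injection from Day 1 predose, so the change includes the other speed's injection, although a Day 2 predose value is scheduled

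*SAP*

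**What the plan says.** SAP 9.4.4 has vital signs and their changes from baseline summarised for each treatment, "where baseline is defined as Day 1 predose". It makes no exception for Part B. SAP 9.1 gives the calculation: "Each individual change from baseline will be calculated by subtracting the individual subject’s baseline value from the value at the timepoint". That is one baseline per subject, not one per injection. SAP 6 lists slow and fast injection as separate treatments (Tests 2 and 3 for the 2-mL device, Tests 4 and 5 for the 1-mL device), so a summary by treatment is a summary by speed within each volume.

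Protocol 5.4 calls Part B a crossover: "For Part B, a crossover design was chosen as PK analysis is not an endpoint". SAP 5 describes the dosing: "AI dose regimen will be self-administered by slow and fast SC injection(s) on consecutive days (sequence randomized) in the abdomen after an overnight fast".

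The Part B schedule in Protocol Section 2 puts vital signs at 0 and 6 hours on Day 1, at 0 and 6 hours on Day 2, at 24 hours on Day 3, and then on Days 15, 43 and 86. The schedule comment says "Zero-hour collection within 30 minutes before dosing", so the Day 2 entry at 0 hours is a predose reading for the second injection.

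Protocol 10.3.1.2.4 covers vital signs among the other safety parameters and says "changes from baseline (predose) where appropriate, will be listed and summarized". It names no day.

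**The concern.** A change from baseline reported under a treatment is normally read as what happened after that treatment. For a Day 2 injection the SAP's definition does not give that. The starting value precedes a different injection, of the other speed, given the day before. Anything that moved between the two mornings enters the change and is reported under the Day 2 speed: the effect of the first injection, a second night in the unit, familiarity with the procedure.

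At stake is how the vital-sign tables in Part B can be read. Comparing safety and tolerability across injection speeds is the Part B objective, and vital signs are one of the named safety measures. A reader could take part of a day effect for a response to the injection. The data needed to separate the two are already being collected.

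**Working it through.** The documents state no figure on this point, so there is none to reproduce. The check is a reading of the schedule followed by simple arithmetic.

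**How many injections are affected.** Part B has about 36 subjects with two injections each: 36 × 2 = 72. One of each pair is on Day 2: 36/72 = 50%.

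**What the reported change contains.** For a Day 2 injection the 6-hour change under SAP 9.4.4 splits exactly into two parts:

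(Day 2 6 h − Day 1 0 h) = (Day 2 0 h − Day 1 0 h) + (Day 2 6 h − Day 2 0 h)

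The second bracket is the change after the Day 2 injection. The first is the shift between the two predose readings, about 24 hours apart with the other speed's injection in between. The whole covers about 24 + 6 = 30 hours. The 24-hour reading on Day 3 is likewise about 24 + 24 = 48 hours from its assigned baseline.

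**How much of the shift reaches the treatment means.** Let d be the mean of the first bracket. The documents give no value for d; it is an assumption, taken to be the same whichever speed came first. Let N be the subjects in a volume arm and k the number who take the slow injection on Day 2. With both days pooled under each treatment:

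- slow mean change contains (k/N)d
- fast mean change contains ((N − k)/N)d
- slow minus fast contains ((2k − N)/N)d

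N is 18 randomised or 16 completing per arm. The split between sequences is not stated, so a range is shown:

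| N | Slow on Day 2 / fast on Day 2 | In slow mean | In fast mean | In slow − fast |
|---|---|---|---|---|
| 18 | 9 / 9 | 0.500d | 0.500d | 0 |
| 18 | 10 / 8 | 0.556d | 0.444d | 0.111d |
| 18 | 11 / 7 | 0.611d | 0.389d | 0.222d |
| 16 | 8 / 8 | 0.500d | 0.500d | 0 |
| 16 | 9 / 7 | 0.562d | 0.438d | 0.125d |
| 16 | 10 / 6 | 0.625d | 0.375d | 0.250d |

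Under an even split, d = 1, 2 or 5 units moves each treatment's mean change by 0.5, 1.0 or 2.5 units. If the tables show the days separately, the Day 2 rows carry all of d and the Day 1 rows none. Each individual Day 2 change carries that subject's whole shift in either layout.

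**With each injection's own predose value as baseline.** The first bracket drops out, so the contribution of d is 0 in each treatment mean and in slow minus fast, for any split.

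**The case against.** The best defence is that Day 1 predose is the only drug-free predose value in the dosing period. Protocol 3.2 gives a mean half-life of 10.5 days and maximum concentrations 3 days after subcutaneous dosing, so at Day 2 predose exposure to the first dose is still rising. Change from the untreated state is a legitimate safety question. This stands, and it is why the Day 1 change should be kept. It does not make that change a measure of the response to the second injection, and the SAP does not offer this reasoning.

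It is also fair that vital signs are only described. The listed Part B comparisons of slow with fast concern pain scores, and no decision rule uses vital signs. Values are summarised and listed alongside the changes. If the Day 2 0-hour and 6-hour rows both appear under the Day 2 treatment and data are complete, the mean within-day change can be recovered by subtraction, though its standard deviation cannot.

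Four stronger readings are tempting, and the documents do not support them:

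- **The slow-fast comparison is biased.** Order is randomised, and with an even split and a common shift the contribution to the mean difference is 0. Only an uneven split leaves a remainder, as tabulated.
- **The protocol is contradicted.** Its wording is qualified and names no day. Day 1 predose is a predose value.
- **The 24-hour summary loses half its subjects.** The schedule labels only the Day 3 reading as 24 hours, so a table built from labels, with an even sequence split, would hold about 9 of 18 subjects per speed. The SAP does not say tables are built that way, and detailed displays are left to a separate shell document.
- **The changes are noisier.** The documents give no variances or correlations from which to judge this.

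**Conclusion.** The point holds and is minor. Followed as written, SAP 9.4.4 gives about 36 of 72 Part B injections a change from baseline that includes the other speed's injection and any drift between the two mornings, while a reading taken shortly before the injection goes unused as a baseline. Under an even sequence split, half of any Day 1 to Day 2 shift enters each treatment's own mean change and none enters the mean slow-minus-fast difference.

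This rests on the planned numbers, on tables that pool both days under a treatment, and on a shift that does not depend on which speed came first. The size of the shift is unknown, so the effect in measured units is illustrative only. Part A has one dosing day and is unaffected.

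**What to change.** Amend SAP 9.4.4 for Part B as follows.

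1. For each injection's acute changes (same day and 24 hours), define baseline as the 0-hour predose value on that injection's day.
2. State that the Day 2 0-hour reading serves both as baseline for the Day 2 injection and as the 24-hour value for the Day 1 injection.
3. Keep change from Day 1 predose as a supplementary summary of cumulative change from the drug-free state.
4. Use the Day 1 baseline for the Day 15, 43 and 86 readings. These follow both injections, so summarise them by volume arm and not by speed.

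Leave Part A as it is.

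The cost is a few sentences, a programming flag and one extra summary; every value is already scheduled. The downside is that the Day 2 baseline is not drug-free and carries any residual effect of the first injection. The retained Day 1 summary lets the reader see that effect.
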